3.4 Treatment Discontinuation Date and Intercurrent Event Date

The concept of intercurrent event is one of the estimand attributes as defined in Section 8.1.2 and Section 8.1.3. For non-responder imputation (NRI) analyses of binary efficacy endpoints, the intercurrent event date will be defined as the date of treatment discontinuation due to any reason. For multiple imputation (MI) analyses of binary efficacy endpoints, the intercurrent event date will be defined as the date of treatment discontinuation due to AE (including death) or lack of efficacy, while for the multiple imputation analyses of continuous and categorical efficacy endpoints (including the reference-based and hypothetical MI analyses), the intercurrent date will be defined as the date of treatment discontinuation due to any reason. Since treatment discontinuation date is not collected, the treatment discontinuation date is defined as:

Treatment end date + dosing interval (28 days) + visit window (3 days for DBTP, 4 days for the MP)

With “Treatment end date” derived from the “Study Medication Discontinuation” CRF.

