Unless stated otherwise, statistical tests of efficacy variables will be performed 2-sided and p-values will be rounded to 4 decimal places. P-values less than 0.0001 will be presented as “<0.0001” and p-values greater than 0.9999 will be presented as “>0.9999.” Statistical comparison will be performed at the 0.05 level of significance.

The SAS® outputs supportive of any inferential statistics that are part of the hierarchical testing procedure (ie, all inferential statistics associated with the endpoints in figure 4.1) will be provided as a separate PDF document in addition to TFLs. These outputs will be included in the ‘Documentation of Statistical Methods’ section of the clinical study report.

Unless specified differently in the SAP, the order of treatment groups to be presented in tables from left to right will be:

- Placebo
- Bimekizumab 160mg Q4W

Selected tables may include columns for:

- all study participants, regardless of study treatment
- all study participants on bimekizumab, regardless of whether they shifted from placebo after the Double-Blind Treatment Period or not
- study participants randomized on placebo who shifted to bimekizumab after the Double-Blind Treatment Period

The abbreviation for bimekizumab is BKZ and will be used in tables and listings headers. In the TFLs study participants on bimekizumab 160mg will be displayed as “BKZ 160mg Q4W”.

All study participants dosed with bimekizumab will be summarized in some TFLs in a treatment column labeled as “BKZ 160mg Q4W Total”.

For all TFLs not dedicated to the Double-Blind treatment period only, the Placebo-randomized study participants who shifted to bimekizumab after the Double-Blind Treatment Period will be summarized in a treatment column labeled as “Placebo / BKZ 160mg Q4W”.

Per protocol,

- visit windows of ± 3 days are permissible for all visits through Week 16 (included). The visit window is relative to the Baseline Visit.
- visit windows of ± 4 days are permissible for all visits after Week 16,
- for the SFU Visit, the visit should occur no more than 3 days prior to the scheduled visit date and within 7 days after the scheduled visit date.

Only data collected at the scheduled visit will be included in the analysis. The only deviations may concern PK data, unscheduled vendor data collected with a few days of delay, and MRI data (see below).

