Multiple imputation will be applied on missing data, and data that are collected after the date of intercurrent event (IE) as defined in Section 3.4. If there are fewer than 3 components with observed data (considering all observed data after the IE date as missing), each of the components will be imputed separately before deriving the response; the available observed values and the imputed values will be used to derive the response. Study participants with IEs, will then be considered non-responders at all time points after the IE date. Analysis details are presented in Section 4.2.1.4.2 and Section 8.1.4.4.

- The tipping point approach:

The tipping point approach implemented if the primary endpoint analysis result is statistically significant at alpha=0.05. The tipping point approach will first include a Worst Case imputation:

- All data after the date of IE for treatment discontinuation due to any reason will be set to missing.
 - If at least 3 of the 4 components have observed data collected and where possible, the ASAS response/non-response will be calculated based on observed data.
 - If fewer than 3 components have observed data, then study participants treated with bimekizumab will be classed as non-responders, while study participants treated with placebo will be classed as responders.

If the significant result remains, then no further analysis is necessary.

- If the result changes as a result of the worst-case approach, then imputation with delta adjustments will be made to each missing component before deriving the ASAS endpoint to establish the 'tipping point' at which the result changes.

A similar approach to that described above for the Modified Composite Estimand - Multiple Imputation will be implemented for the Delta Adjustment approach. However, study participants with treatment discontinuation will not be automatically considered non-responders at all timepoints after the IE date. Instead, missing data and data after the IE date for treatment discontinuation for any reason will be imputed and adjusted, and the imputed and adjusted data will be used, together with observed data, to derive the response. These approaches are described in detail in Section 4.2.1.8 and Section 8.1.4.7.

- The treatment policy strategy:

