7 MEASUREMENTS OF TREATMENT COMPLIANCE

Due to the method of administration of the treatments, compliance will be examined in terms of completed injections. Treatment compliance will be calculated as:

$$\frac{\text{Total number of actual (completed) injections}}{\text{Total number of expected injections}} \times 100\%$$

The total number of expected injections is derived relative to when the study participant finishes treatment. If a study participant completes treatment, four injections are expected during the Double-Blind Treatment Period and nine during the Maintenance Period. A total of thirteen injections are then expected (at Baseline, and at each study visits from Week 4 until Week 48). If a study participant discontinues early, then the number of expected injections is based on the time of early discontinuation relative to the dosing visits.

A summary of percent treatment compliance categorized as <75% and $\geq 75\%$ will be provided by treatment group, as well as a by-study participant listing of treatment compliance.

Compliance will be summarized on the SS for the Double-Blind Period, on the MS for the Maintenance Period and on the SS for the overall period.

Injections missed due to COVID-19 will be summarized and tracked in the listings.

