8.1.4.4 Analysis using modified composite estimand - MI

A supportive analysis will evaluate the modified composite estimand (Section 4.2.1.4.2) that combines the clinically meaningful improvement from Baseline in ASAS40 response at Week 16 and the intercurrent event of not discontinuing early from study treatment due to AE or lack of efficacy prior to Week 16.

The same logistic regression model as the one used for the primary efficacy analysis will be used on the RS. The following 4 attributes describe the estimand that will be used to define the treatment effect of interest for this analysis:

- Population = Study participants enrolled according to the protocol-specified inclusion/exclusion criteria and randomized to IMP
- Study participant-level outcome = ASAS40 at Week 16
- Intercurrent event handling = An intercurrent event is defined as discontinuation of study treatment due to AE (including death) or lack of efficacy, prior to Week 16. A composite strategy will be implemented in which a positive clinical outcome is defined as achieving ASAS40 at Week 16 and not discontinuing study treatment due to AE or lack of efficacy through Week 16.
- Population-level summary measure = Conditional odds ratio comparing bimekizumab to placebo.

Intercurrent events (Section 3.4) will be acknowledged as an unfavorable outcome for this modified composite estimand in considering study participants with intercurrent events as ‘non-responders’ to the study treatment.

Missing data at Week 16 that are not preceded by an intercurrent event will be imputed by standard MI techniques. Refer to Section 4.2.1.2 for further details.

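### In the supportive modified composite MI analysis, a death or a stop for AE or lack of efficacy after the Week 12 dose, with no Week 16 assessment, can be imputed as a response

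*SAP*

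**What the plan says.** Section 3.4 explains why the date is derived: "Since treatment discontinuation date is not collected, the treatment discontinuation date is defined as" the sum "Treatment end date + dosing interval (28 days) + visit window (3 days for DBTP, 4 days for the MP". Treatment end comes from the Study Medication Discontinuation CRF. For MI analyses of binary endpoints, "the intercurrent event date will be defined as the date of treatment discontinuation due to AE (including death) or lack of efficacy".

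Section 8.1.4.4 describes the modified composite estimand for ASAS40: "An intercurrent event is defined as discontinuation of study treatment due to AE (including death) or lack of efficacy, prior to Week 16". It defines success as reaching ASAS40 at Week 16 without having stopped for AE or lack of efficacy up to that visit. It then adds: "Missing data at Week 16 that are not preceded by an intercurrent event will be imputed by standard MI techniques".

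Section 4.2.1.1 gives the operational rule: "Study participants with IEs, will then be considered non-responders at all time points after the IE date". Sections 4.2.1.4.1 (Step 3) and 4.2.1.4.2 repeat it, switching to non-response only at visits later than the event date.

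In Table 4-1 this analysis is supportive for the primary endpoint and for the binary endpoints in the testing hierarchy. It is also used for the other binary endpoints.

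**The concern.** The point of the modified composite estimand is that deaths and stops for AE or lack of efficacy count as failures, while other missing data are imputed. That works only if the event is dated before the visit being scored. Adding 31 days to the last dose pushes the date to Week 16 or beyond for anyone whose last dose was at Week 12. If that participant has no Week 16 value, nothing in the operational rules makes the outcome a failure. The missing components go into the imputation model and may come out as a response, even for a participant who has died. The definition in Section 8.1.4.4 and the rules meant to implement it then give different answers for the same person.

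**Working it through.** **Inputs**
- Event date = treatment end + 28 + 3 = treatment end + 31 days in the double-blind period (Section 3.4). Assumption: treatment end is the date of the last dose. If the CRF holds a later date, the event date moves later and the gap widens.
- Day 1 is the day of first dose (Section 3.2.1.1).
- Section 7: "four injections are expected during the Double-Blind Treatment Period and nine during the Maintenance Period". The double-blind doses are therefore at Baseline and Weeks 4, 8 and 12.
- Section 3.1 sets a tolerance of plus or minus: "3 days are permissible for all visits through Week 16 (included). The visit window is relative to the Baseline Visit". Week 12 is Day 85 (82 to 88) and Week 16 is Day 113 (110 to 116).

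**Dates**
- Last dose at Week 12: 82 + 31 = 113; 85 + 31 = 116; 88 + 31 = 119. The event date is Day 113 to 119. It equals nominal Week 16 for a dose on Day 82 and is later for the other six permitted dose days. Week 16 is never after the event date.
- Last dose at Week 8 (Day 54 to 60): 54 + 31 = 85; 60 + 31 = 91. Week 16 falls after the event date and is correctly a failure.
- The SAP does not say which date stands for a missed Week 16 visit. If the end of the window (Day 116) were used, doses on Days 82 to 84 would give event dates of Day 113 to 115, and Week 16 would fall after them. Doses on Days 85 to 88 (event dates Day 116 to 119) would still not be covered, and Day 85 is the on-schedule day.
- The mechanism also operates at earlier visits within 31 days of the last dose. With a dose on Day 1 and death on Day 20, the event date is Day 1 + 31 = Day 32. Week 4 is Day 29, so the Week 4 response is imputed.

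**Size**

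The SAP gives no stop rates. Assume 3%, 5% or 8% of each arm stop for AE or lack of efficacy, spread evenly over the four dosing intervals, and that none of those in the last interval has a Week 16 value. Impute at the planning rates in Section 2.4.1: 40% on bimekizumab and 15% on placebo.
- Share of each arm affected = stop rate / 4 = 0.75%, 1.25%, 2%. On bimekizumab this is 1.5, 2.5 or 4 of 200.
- Added to the bimekizumab rate = share x 0.40 = 0.3, 0.5, 0.8 points.
- Added to the placebo rate = share x 0.15 = 0.11, 0.19, 0.30 points.
- Net = share x (0.40 - 0.15) = 0.19, 0.31, 0.50 points.
- Crude odds ratio at 2% affected in each arm: (0.408/0.592) / (0.153/0.847) = 3.82, against (0.40/0.60) / (0.15/0.85) = 3.78 if these stops are failures.

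**The plan's own figure**

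The stated power of over 99% for the primary endpoint reproduces (40% against 15%, 200 against 100, two-sided 0.05: 99.6% with continuity correction). It does not depend on this point.

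**The case against.** The best defence is that 28 days plus a window is a coherent convention for four-weekly dosing. The Week 12 dose is the last double-blind dose and the Week 16 dose follows the Week 16 assessments, so a participant dosed at Week 12 has missed no double-blind dose and is still covered at Week 16. Section 8.1.4.4 also refers to Section 3.4 for its intercurrent events, so the two could be said to agree. This stands as a reason to keep an observed Week 16 value. It does not justify drawing a possible response for someone who has died, or who stopped for AE or lack of efficacy and was not assessed, when success is defined as having had no such stop up to Week 16.

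Other objections limit the point, and they stand:
- Few participants are affected. Section 3.2.3 maps an early-termination assessment made after the Week 12 visit to Week 16, participants who stop treatment are encouraged to keep attending, and three of four components suffice for ASAS40.
- Imputing at the arm's average rate is probably too generous. The model conditions on each participant's own earlier values (Section 4.2.1.4.1), so someone stopping with poor Week 12 scores would be imputed from those scores.
- For ASAS40, if the primary result is significant, the worst-case step of the tipping point analysis treats missing bimekizumab responses more harshly than any correction here.

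A reader might extend the point to Week 52, where a Week 48 dose gives Day 337 + 32 = Day 369 against Day 365. That adds little: Section 3.2.2.1.1 makes Week 48 the final dose, so after it no scheduled dose remains to be stopped and only a death is a clear case.

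**Conclusion.** The inconsistency is real and confined to the supportive modified composite MI analysis. As written, a death or a stop for AE or lack of efficacy after the Week 12 dose, without a Week 16 or mapped early-termination assessment, can be scored as a response, contrary to the definition of success in Section 8.1.4.4. The same can happen at earlier visits within 31 days of the last dose, most clearly for deaths.

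The effect is small. The 0.3 to 0.8 points in the bimekizumab arm are upper bounds under the assumed stop rates, and the 0.2 to 0.5 points net also assume equal stop rates in the two arms. The actual number is not in the document.

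Two stronger inferences are not supported. One is that the primary result is at risk. Section 8.1.2 codes a missing Week 16 response as failure whatever the event date, and Section 8.2.2 applies the same approach to the binary key secondary endpoints. The other is that the error must favour bimekizumab, or the arm with more AE stops. Imputation is run by arm, so equal affected proportions imputed at the planning rates would favour bimekizumab. Lack-of-efficacy stops also count, however, and if placebo had enough of them the shift would shrink or reverse. The direction depends on the balance of stops and on the imputed rates.

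**What to change.** Reconcile Sections 3.4, 4.2.1.4 and 8.1.4.4 with two statements:
1. A participant whose Study Medication Discontinuation CRF gives AE (including death) or lack of efficacy as the reason, and who has no observed or mapped assessment at a visit after the last dose, is a non-responder at that visit and is not imputed.
2. For deaths, the event date is the earlier of the Section 3.4 date and the date of death.

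Leave the handling of observed and early-termination-mapped values unchanged. Making the early-termination date itself an event date would collide with the mapping in Section 3.2.3. One consequence should be accepted openly: two participants with the same kind of stop after Week 12 may be classified differently according to whether one was assessed.

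The cost is SAP wording. The SAP already uses the reason for stopping and the date of death elsewhere. The supportive responder rate may fall slightly; the primary analysis does not change.

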3.5 Protocol deviations

Important protocol deviations (IPD) are deviations from the protocol which potentially could have a meaningful impact on study conduct or on the primary efficacy, key safety, or PK outcomes for an individual study participant. The criteria for identifying IPD will be defined within the appropriate protocol-specific document. IPD will be reviewed as part of the ongoing data cleaning process and data evaluation. IPD will be identified and documented prior to unblinding to confirm exclusion from Per-Protocol Set (PPS) and Pharmacokinetics Per-Protocol Set (PK-PPS).

Since the PPS will be used for a supportive analysis of the primary endpoint which is assessed at Week 16, the exclusion from PPS is limited to the double-blind period, ie, only study participants with IPD or a decrease in dosing or dosing frequency of axSpA background medication due to intolerance/ AE/ side-effects, as permitted per study protocol, with potential impact on primary efficacy endpoint prior to and at Visit 8 (Week 16) can be excluded from the PPS. Study participants with IPD or a protocol-permitted decrease in dosing or dosing frequency of axSpA background medication due to intolerance/ AE/ side-effects, as permitted per study protocol, with potential impact on primary efficacy endpoint after Visit 8 (Week 16) will not be excluded from the PPS.

Also, an IPD will not always necessitate the removal of a study participant from the PPS. Depending on the type of protocol deviation, the study participant may remain in the PPS. The protocol deviation specification document developed by the clinical study team should clearly state which deviations will result in a removal from the PPS. See details in Section 3.6.6.

The impact of the COVID-19 pandemic on study procedures/conduct (eg, missed visits, remote visits, interruption of study treatment) will be documented using the information collected on a dedicated eCRF page.

3.6 Analysis sets

The primary efficacy variable will be analyzed for all study participants in the Randomized Set (RS), and supportive analyses of the primary efficacy variable will be performed on the Full Analysis Set (FAS) and the PPS. All other efficacy variables will be based on the RS

Demographics tables will be performed on the RS as well as on the Safety Set (SS), if SS is different from RS. Safety variables will be summarized on the SS. PK variables will be analyzed for all study participants in the safety set and/or PK-PPS.

The analysis sets are defined in the following sections.

3.6.1 Enrolled Set

The Enrolled Set (ES) consists of all study participants who have given informed consent.

3.6.2 Randomized Set

The Randomized Set (RS) consists of all randomized study participants.

3.6.3 Safety Set

The Safety Set (SS) consists of all randomized study participants who received at least one dose of the IMP.

3.6.4 Maintenance Set

The Maintenance Set (MS) will consist of all study participants who have received at least 1 dose of bimekizumab treatment in the Maintenance Treatment period.

3.6.5 Full Analysis Set

The Full Analysis Set (FAS) consists of all randomized study participants who received at least one dose of the IMP and have a valid measurement of all components of the primary efficacy variable at Baseline.

3.6.6 Per Protocol Set

The Per-Protocol Set (PPS) consists of all study participants in the RS who had no important protocol deviations affecting the primary efficacy variable. Important protocol deviations will be predefined and study participants with important protocol deviations will be evaluated during ongoing data cleaning meetings prior to unblinding of the data. See Section 3.5 for further details. Exclusions from the FAS will be considered important protocol deviations that also result in exclusion from the PPS. Additional exclusions from the PPS due to protocol-permitted decrease in dosing or dosing frequency of axSpA background medication due to intolerance/AE/side-effects may also be possible in case a potential impact on the primary endpoint cannot be excluded.

In addition, if after unblinding it is determined that there are study participants who were dosed with bimekizumab in place of placebo, then these study participants will be removed from PPS. Study participants who received a single dose with placebo in place of bimekizumab will remain in the PPS, but participants that received more than a single dose with placebo (or received one dose with placebo and also missed one or more additional doses, therefore fulfilling the IPD criteria of more than 1 missed dose up to week 12 during double-blind phase) when randomized to bimekizumab will be excluded from the PPS.

3.6.7 Pharmacokinetic Per-Protocol Set

The Pharmacokinetic Per Protocol Set (PK-PPS) consists of all randomized study participants who received at least one dose of the IMP and provided at least one quantifiable plasma concentration post-dose (after first IMP administration) without important protocol deviations that would affect the concentration of all samples obtained.

3.6.8 Immunogenicity Safety Set

ADAb and NAb analyses will use the safety set defined above. In the event that sample exportation in China is not approved, thereby preventing the NAb and ADAb analyses of samples of Chinese participants in the specified laboratories located outside of China, a separate immunogenicity safety set will be defined to include all randomized study participants, excluding China participants, who received at least one dose of the IMP.

3.6.9 COVID-19 Free Set

The COVID-19 Free Set (CFS) will consist of all study participants in the RS who had no COVID-19 impact on the primary efficacy endpoint up to Week 16. This will be defined as study participants neither having:

- a COVID-19 related IPD,
- nor a data entry on the COVID-19 impact eCRF,
- nor a COVID-19 related AE (See Section 10.2.4 for definition).

3.7 Treatment assignment and treatment groups

It is expected that study participants receive treatment as randomized for the Double-Blind Treatment Period, or as assigned per protocol study design (via reallocation) for the Maintenance Period.

Hence safety analyses will be based:

- on the SS as randomized, for the Double-Blind Treatment Period (displaying data under Placebo and BKZ 160mg Q4W columns),
- on the MS as assigned treatment, for the Maintenance Period (displaying data under BKZ 160mg Q4W Total column),
- on the SS as randomized/assigned treatment for the overall period (displaying data under BKZ 160mg Q4W Total column),

However, if after unblinding it is determined that study participants randomized to placebo received bimekizumab at any time during the Double-Blind-Treatment Period, then for safety analyses these study participants will be reallocated to the bimekizumab treatment group. Study participants randomized to bimekizumab will only be reallocated to the placebo treatment group if they never received bimekizumab. For AE analyses, AEs for each study participant will be summarized based on the treatment at the onset of each particular AE. AEs that occur on the day of first IMP administration will be allocated to the treatment received on that day. For study participants randomized on placebo who switch treatment per study design at Week 16 (ie, reallocation to bimekizumab treatment), AEs will be allocated to the treatment the study participant was on the day the event occurred. If the event occurs on the day of the switch, it will be attributed to the initial treatment (ie, Placebo), unless the AE fulfills the criteria for an

anaphylactic reaction in which case it will be attributed to the new treatment (ie, bimekizumab). Specifically, this includes events meeting any of the following criteria:

- Events that fulfil the anaphylactic reaction criteria for acute events (refer to [Appendix 1](#))
- Events, that fulfil the hypersensitivity reaction criteria
- Events with an HLT of 'Administration site reactions NEC'
- Events with an HLT of 'Injection site reaction'

Efficacy analyses will be performed according to randomization and not actual treatment received. That is, if after unblinding it is determined that study participants randomized to placebo received bimekizumab at any time during the Double-Blind-Treatment Period efficacy analyses for these study participants will not be reallocated to the bimekizumab treatment group.

Hence efficacy analyses will be based:

- on the RS as randomized, for the Double-Blind Treatment Period (displaying data under Placebo and BKZ 160mg Q4W columns),
- on the RS as randomized/assigned treatment for the overall period (displaying data under Placebo/BKZ and BKZ 160mg Q4W columns).

The description of all efficacy analyses is detailed in [Section 8](#).

